16 ETHICS REVIEW BOARD

It is the responsibility of the Sponsor to obtain approval of the study protocol/protocol amendments, the patient information and the Informed Consent from the ERB before enrolment of any subject into the study.

The study medication will not be delivered to the study centers until approval from the ERB has been obtained.

The Sponsor shall report all SUSARs also to the ERB, unless otherwise agreed. If a study stops prematurely at a study center for any reason, the ERB must be informed. At the end of the study, the Sponsor should notify the ERB. The Sponsor should file all correspondence with the ERB.

16.1 ETHICAL CONDUCT OF THE STUDY

The study will be conducted in accordance with the protocol, applicable regulatory requirements, GCP and the ethical principles of the Declaration of Helsinki as adopted by the 18th World Medical Assembly in Helsinki, Finland, in 1964 and subsequent versions (Appendix 23.1).

16.2 RISK - BENEFITS

A risk analysis for this study has been made. These risks together with the actions to minimize these risks are compiled below:

	Anticipated risk	Action
1	Side effects such as minor behavior problems (mood changes), sleep disturbances, nausea or vomiting	Reported as Adverse Events and follow up until recovered. A Development Safety Update Report (DSUR) will be presented yearly to MPA
2	Trauma for the child to take medicine	Capsules may be opened and the content can be mixed with something tasty. The study nurse will instruct the parents/guardians when study medication is distributed and will also follow up how it works by telephone calls one and two weeks after Baseline
3	No effect on the recovery rate	There is no alternative treatment, why there is no risk that the patient looses an effective treatment by participating in the study

A short-course oral treatment with corticosteroids (defined as 1-2 mg/kg once daily in 7-14 days) is not associated with major side effects, such as risk of growth retardation, osteoporosis or diabetes mellitus in children, but may be associated with minor side effects, such as behavioral problems (mood changes), sleeping disturbances, nauseas or vomiting in 4,3 – 5,4 % of cases (17,25,26).

The risk of minor side effects will be reduced with the dose $1 \text{ mg/kg} \times 1$ (17), as we plan on using in the present study.

Increased susceptibility to infection (<1%) is the most frequent (S)AEs associated with short courses of corticosteroids (25,26). In five large RCTs on short-course corticosteroid treatment, three children with varicella infection needed intensive care due to complications (25).

Parents/guardians will be informed before start of treatment in the current study about the importance to attend health care if fever or signs of infection occur during the study period.

In summary, the benefits, i.e. possibly improved recovery of the facial nerve palsy are anticipated being higher than the risks.

16.3 PATIENT INFORMATION AND INFORMED CONSENT

It is the responsibility of the Investigator to provide each participant with full and adequate verbal and written information about the objectives, procedures and possible risks and benefits of the study. All participant will be given the opportunity to ask questions about the study and will be given sufficient time to decide whether or not to participate in the study. All information about the study will be age-adjusted in order to obtain good adherence for both younger and older children and adolescents.

The written patient information must not be changed without being approved by the Ethics Review Board.

The participant will be notified of their voluntary participation and of their freedom to withdraw from the study at any time and without giving any particular reason. participant must also be informed that withdrawing from the study will not affect their future medical care, treatment or benefits to which the participant is otherwise entitled.

Parents/guardians will sign the informed consent for children 1-17 years of age.

The Investigator is responsible for obtaining written Informed Consent from all parents/guardians prior to enrolment in the study. If only one parent/guardian is present at the visit, the other parent/guardian will be contacted by telephone, informed about the study, given the chance to ask questions and sent an ICF by email. The signed ICF will then be sent back by e-mail, or as a photocopy on the mobile phone, to the Investigator and saved in the Investigator's file until the original ICF is returned.

The parents/guardians will consent to:

- Participating in the study.
- Personnel from the sponsor or the regulatory authorities to gain full access to hospital records to check the quality of data collected in the study.
- Recording, collection and processing of data and storing of data in a database.
- Possible transfer of information from the study to countries outside the European Union (EU).

It should be clearly stated that the data will not identify any participant taking part in the study, in accordance with the European General Data Protection Regulation (GDPR) (2016/679/EU).

A copy of the patient information and the ICF will be given to the parents/guardians. The Investigator (or a co-Investigator) who gave the verbal and written information to the participant will sign the ICF. The Investigator will file the signed ICFs in the Investigator's File.

17 DATA HANDLING AND RECORD KEEPING

17.1 CASE REPORT FORMS

CRFs are required and should be completed for each included participant. The child's identity must always remain confidential.

Paper CRFs will be used and study data will be entered in a database at the Sponsor (Center for Clinical Research Dalarna). The completed study database is the sole property of the Sponsor and will not be made available in any form to third parties (except for authorized representatives of appropriate regulatory authorities) without written permission from the Sponsor.

The Investigator is responsible for ensuring the accuracy, completeness, legibility and timeliness of the data recorded in the CRF. Corrections to the CRF must be signed by the Investigator or a designated representative.

17.2 RECORD KEEPING

To enable audits and inspections by regulatory authorities, the Investigators will keep records (essential documents) of the study for at least 10 years. This includes any original source data related to the study, the subjects identification list (with subject numbers, full names and personal numbers), the original signed ICFs, copies of all CRFs and detailed records of study medication disposition.

The Sponsor is also, as per GCP-requirements, responsible for archiving their part of the study documentation.

18 INSURANCE

Patients participating in this study are covered by the Swedish Patient Insurance (Patientskadeförsäkringen LÖF-Landstingens Ömsesidiga Försäkringsbolag) and the Swedish Pharmaceutical Insurance (Läkemedelsförsäkringen).

19 PUBLICATION POLICY

All information not previously published concerning the clinical study is considered as confidential and will remain the sole property of the Sponsor. The Investigator agrees to use this information only in connection with this study and will not use it for other purposes without written permission from the Sponsor.

After completion of the study, the statistical analyses will be performed and the results will be presented to the Investigators. Based on these data, the Sponsor, in cooperation with the Investigators, will prepare a clinical study report. The report will be submitted to the MPA and may form the basis for a manuscript intended for publication in a medical/scientific journal.

20 SUPPLEMENTS

20.1 CHANGES OF THE STUDY PROTOCOL

No change in the study procedures will be effected without the mutual agreement of the Investigators and the Sponsor (except where necessary to eliminate an immediate hazard to subjects). All changes of the final study protocol must be documented by signed protocol amendments. If substantial changes to the design of the study are made, the MPA and the ERB will be notified for review and approval.

20.2 APPLICATION TO REGULATORY AUTHORITIES

Prior to initiating the clinical study, the Sponsor will submit an application for authorization to conduct the study, including all required documents, to the MPA. Additional documentation may be demanded for investigational products with special characteristics.

One complete application will be submitted. For each planned study center, the address and the name and position of the Investigator will be indicated on the application.

20.3 STAFF INFORMATION

It is the responsibility of the Investigator to ensure that all personnel involved in the study are fully informed of all relevant aspects of the study, including detailed knowledge of and training in all procedures to be followed.

20.4 CRITERIA FOR TERMINATION OF THE STUDY

The Sponsor reserves the right to discontinue the study prior to inclusion of the intended number of subjects, but intends to exercise this right only for valid scientific or administrative reasons. After such a decision, all delivered unused investigational products and other study-related materials must be collected and all CRFs must be completed as far as possible.

The study can be prematurely discontinued in the following cases (examples):

- Unexpectedly high proportion of adverse events, possibly or probably related to the study medication.
- New findings about the investigational product(s) that changes the benefit/risk ratio.
- Study protocol is difficult to cope with.
- Recruitment of eligible subjects is far too low.
- Problems with manufacturing or stability of the investigational product(s).
- Unacceptable low Investigator, Sponsor or subject compliance.
- Critical change in personnel, administrative or scientific standards at the Sponsor or at the study centers.
- No significant result will be obtained as anticipated.

21 **REFERENCES**

- 5. Läkemedelsverket. Läkemedelsbehandling av Borreliainfektion ny rekommendation. 2009 [updated 2013-12-03; cited 2016-05-24].

23 APPENDICES

- 23.1 DECLARATION OF HELSINKI
- 23.2 RATING SCALES OR DIARIES FOR ASSESSMENT OF EFFICACY OR SAFETY
- 23.3 LABELING OF INVESTIGATIONAL PRODUCTS

## 1. Version History

Version	Date	Reason for Change
Draft 1.0	2022-02-24	
Draft 1.0	2022-04-13	See previous version

## 2. Introduction

The aim of this statistical analysis plan (SAP) is to describe details of planned presentation of the study data described to be performed by the UCR (Uppsala Clinical Research) Statistics section. The results will be presented according to the output specification (see Appendix 1 Output Shells). The UCR study biostatistician is responsible for writing the plan with necessary input from other members of the study team. A biostatistician not otherwise involved in the study together with the sponsor will approve the final version.

The SAP is based on the study protocol “CLINICAL STUDY PROTOCOL\_\_FACE\_01\_version 2.3.docx”

## 3. Abbreviations

AE	Adverse Events
AUC	Area under the curve
CI	Confidence Interval
CKF	Center for Clinical Research, Dalarna
CRF	Case Report Form
FACE	Facial nerve palsy and cortisone evaluation in children study
FaCE-scale	Facial Clinimetric Evaluation Scale
FDI	Facial Disability Index
HB	Houce_Brackmann scale
ITT	Intention to treat
NeBoP	Clinical neuroborreliosis prediction test
PP	Per Protocol
PROMs	Patient/parent reported outcome measures
LOCF	Last Observation Carried Forward
SAE	Serious Adverse Events
SAQ	Synkinesis Assesment Questionnaire
SB	Sunnybrook scale
SD	Standard Deviation
SEM	Standard Error of the Mean
SBPS	Scandinavian Bell's Palsy Study
SUSAR	Suspected Unexpected Serious Adverse Reaction
UCR	Uppsala Clinical Research Centre

#### 4. Background

In the Swedish pediatric populations about 5-21/100 000 children per year suffer from acute facial nerve palsy, which relates to a swollen and dysfunctional facial nerve. However, no efficient evidence-based treatment/clinical guidelines exist for these affected children. The purpose of this project is therefore to evaluate the efficacy of cortisone treatment (prednisolone) given to children with acute facial nerve palsy in a randomized placebo-controlled trial (RCT). We hypothesize that prednisolone will improve clinical outcome for children with facial nerve palsy, even after that no further spontaneous improvement is expected (12 months) by reducing inflammation and swollenness of the facial nerve.

#### 5. Study Objectives and Endpoints

##### 5.1. Objectives

###### 5.1.1. Primary Objective(s)

The primary objective of this study is to evaluate the efficacy of cortisone versus placebo treatment in children with acute facial nerve palsy, measured as physician assessed recovery with the House-Brackmann grading scale.

###### 5.1.2. Secondary Objective(s)

The secondary objectives are:

- to evaluate the total recovery rate at 1 month as compared to the total recovery rate at 12 months, in order to evaluate if prediction of recovery at 1 month is feasible and/or useful in children with acute facial nerve palsy
- to evaluate subjective symptoms and influence in daily life in children with acute facial nerve palsy
- to evaluate the safety profile for cortisone in children with acute facial nerve palsy

##### 5.2. Endpoints

###### 5.2.1. Primary Endpoint(s)

The primary endpoint is the total recovery rate at 12 months follow-up in the two treatment groups measured with the House-Brackmann scale.

###### 5.2.2. Primary outcome measure

The physician performed House-Brackmann grading scale (1 is normal and 6 is total loss of function) is chosen as primary outcome measure in the FACE study, since it is a valid and easy to perform grading scale for evaluation of facial nerve function and it has most

frequently been used in previous studies. The primary outcome measure (recovery) is defined as House-Brackmann grade 1 at 12 months follow-up. The time point for the primary outcome is chosen as no further spontaneous recovery of the facial nerve function is expected after 12 months and it is used in previous studies.

#### 5.2.3. Secondary Endpoint(s)

Secondary endpoints are:

- the total recovery rate at 12 months follow-up in the two treatment groups measured with the Sunnybrook scale.
- The Sunnybrook scale (100 is normal function and 0 is total loss of function) is another objective scale for grading the facial nerve function. It will be used as secondary outcome measure. It is validated for children, easy to perform and has been used in previous studies. It correlates well to the House-Brackmann scale and has been shown to be useful for prediction of recovery in adult patients.
- the agreement between the two grading scales for facial impairment (House-Brackmann and Sunnybrook), in order to decide which grading scale has the most preferable utility and should be recommended in pediatric patients
- the total recovery rate at 1 month follow-up as compared to the total recovery rate at 12 months follow-up, measured with Sunnybrook and House-Brackmann scale (prediction).
- quality of daily life at 1 and 12 months follow-up measured with the Facial Clinimetric Evaluation (FaCE) scale and the Facial Disability Index (FDI) and at the 12 months measured with the Synkinesis Assessment Questionnaire (SAQ) and to correlate them to the physician assessed House-Brackmann and Sunnybrook grading scales .
- number of Adverse Events possibly or probably related to the study drug during the 12 months follow-up.

#### 5.2.4. Secondary outcome measures

The physician performed Sunnybrook grading scale (100 is normal and 0 is total loss of function) is chosen as secondary outcome measure as it correlates well to the House-Brackmann scale in adult patients, is easy to perform and evaluates facial function in rest and activity. Both the House-Brackmann and the Sunnybrook grading scale are included in order to be able to evaluate agreement between them, and to decide which one has the best most preferable utility and thus should be recommended for evaluation of facial nerve palsy in children. Sunnybrook has also been used for prediction of prognosis in adult patients and will now be evaluated for prediction of recovery in pediatric patients.

Three validated child/parent assessed instruments for disease specific quality-of-life are chosen as additional secondary outcome measures for patient/parent reported outcome measures (PROMs), in order to examine and better understand facial disability (18-21).

The Facial disability index (FDI) consists of 10 different items (6 is full satisfaction, 1 is no satisfaction) divided into two domains; physical function (with composite score of -25 – 100) and social/well-being function (with a composite score of 0-100) (18).

The Facial Clinimetric Evaluation Scale (FaCE scale) includes 15 items (5 is full satisfaction, 1 is no satisfaction) in six domains and a total composite score of 0-100.

The Synkinesis Assessment Questionnaire (SAQ) includes 9 items concerning defect recovery (1 is full satisfaction, 5 is no satisfaction) and gives composite score of 0-100.

## 6. Study design

The FACE study is a randomized double-blind, placebo-controlled, multicenter trial. The study is a randomized two armed intervention study with several well-defined clinical outcome measures with a superiority hypothesis testing in favor for the intervention (prednisolone).

Children with acute facial nerve palsy (idiopathic or *Borrelia*-associated) will be recruited at 17 study centers during 2019-2023 and followed during 12 months. Inclusion and exclusion criteria are set.

The Principal Investigator (a pediatrician) or a co-Investigator (an Ear-Nose-Throat specialist) will be responsible for performing the objective evaluation of the facial nerve function on admission (or one day after) and at the follow-up visits 1 month and 12-months.

Study nurses will take care of parts of the study work, such as performing the one and two weeks telephone calls, collecting questionnaires from the child/parents/guardians, collecting and entering data in the CRFs and being the main contact person for the monitor.

Participants are randomly assigned to prednisolone or placebo. Content in bottles with study drug are blinded and coded after a randomization list in variable blocks without stratification. Bottles with study drug has been distributed to each study center.

### Intervention:

Prednisolone 1 mg/kg (max 50 mg) per orally once daily in 10 days, given as 5 mg capsules (blinded) based on weight intervals (5 kg) up to > 50 kg.

### Control:

Placebo

End of the study is defined as the 12 months follow-up visit for the last patient.

Table 1. Visit Schedule

	Screening/ Baseline	Telephone call 1 week ± 3 days	Telephone call 2 weeks ± 3 days	Visit 1 month ± 5 days	Visit 12 months ± 2 weeks
Informed consent	X				
Inclusion /Exclusion criteria	X				
Medical history	X				
Demographics	X				
Weight/length/BMI	X				
Physical examination	X				
NeBoP score	X				
House-Brackmann scale	X			X	X
Sunnybrook scale	X			X	X
Concomitant medication	X			X	X
Distribution of study medication	X				
Compliance of study medication		X	X		
Reporting of Adverse Events		X	X	X	X
Return of unused tablets				X	
Facial disability index				X	X
Facial Clinimetric Evaluation Scale				X	X
Synkinesis Assessment Questionnaire					X

## 7. Definition of Analysis Populations

The analysis of data will be based on different subsets according to the purpose of the analysis.

Screening failure	Patients that have been screened but have not received any investigational product, will be considered as screen failures
Withdrawals	Patients that fulfil inclusion criteria and have signed informed consent but withdrew after inclusion (before data were collected)
Intention to treat (ITT)	All randomized patients receiving at least one dose of study drug and have available data. The ITT data set will be used for the safety as well as for the efficacy endpoints
Per Protocol (PP)	The PP comprises data from all subjects randomized and treated with evaluable efficacy data, and no major protocol deviation that significantly affects the evaluability of the subject in the study. The PP will be used for presentation of the primary endpoint only.

NOTE:

Screening failures will not be included in the study database.

For participants considered lost to follow-up, the CRF will be completed up to the last visit performed. Timing of withdrawal or loss to follow-up will be presented for each group and each time point in the CONSORT flow diagram.

Criteria for withdrawal are:

- AE that precludes further continuation of treatment
- No compliance with study procedures
- The patient becomes pregnant
- Other medical to the Investigator
- Patient's decision

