13.2 STATISTICAL ANALYSIS

The statistical methods will be described in detail in a statistical analysis plan (SAP) that will be finalized and approved before data base lock is performed. Statistical testing may be undertaken for hypothesis generating purposes, using two-sided tests and 5% alpha level, unless otherwise stated.

Data will be presented by treatment group (prednisolone/placebo). Graphical methods may be used wherever it is regarded as appropriate.

The last pre-administration observation will be used as the baseline value for calculating post-administration changes from baseline. All data obtained on the CRF Protocol version 2.3_2021-06-04

and entered into the database will be provided in separate data listings showing individual subject values. Tabulations of summary statistics, graphical presentations, and listings will be performed by the UCR statistician. All statistical calculations will be performed using SAS[®] version 9.4 or later (SAS Institute Inc., Cary, NC, USA) or SPSS statistics, version 21 (IBM Corporation, USA).

Intention-to-treat will be applied when analyzing results from the primary outcome. Comparisons between groups for dichotomous endpoints (recovery/no recovery) will be performed using Fisher's exact test and for categorical endpoints (scale) using Mann-Whitney U-test. For correlations between scales, Pearson's correlation test, or Cohen's kappa if appropriate, will be used. When predicting recovery at 1 month to 12 months, diagnostic performance will be calculated on recovery defined as House-Brackmann grade 1. Analysis of early predictors will be performed to understand variance of subgroups. Furthermore, logistic regression analysis will be used to evaluate recovery in relation to baseline data.

Study patients that have been screened but not received any study medication, will be considered as screen failures and will not be included in the study database.

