### 8.3. Treatment Administration/Compliance

The intervention is treatment with either prednisolone (capsule Prednisolone 5 mg), 1 mg/kg once daily in 10 days or control treatment (capsule placebo) once daily in 10 days. The number of capsules is based on the child's weight and presented in the table below:

Child's weight /kg	Number of capsules/day	Total number of capsules
5 - 9.9	2	20
10 - 14.9	3	30
15 - 19.9	4	40
20 - 24.9	5	50
25 - 29.9	6	60
30 - 34.9	7	70
35 - 39.9	8	80
40 - 44.9	9	90
>45	10	100

Capsule Prednisolon 5 mg (APL), dosage 1 mg/kg (max 50 mg) once daily for 10 days according to pre-calculated weight. All bottles include 100 capsules.

Compliance for the 10 day period:

Compliance (0-100%) = (Number of tablets actually taken x 100)/total number of capsules

Patients with treatment compliance less than 70% will be excluded from the PP analysis. Patients with 0% compliance will be excluded from ITT analysis.

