## 12. Description of Derived Variables

Duration of AE: stop date minus onset date expressed in days

Variable	Algorithm in words	SAS Variable name
Complete recovery of palsy at month 1 according to SB scale	Healed (1) if sunnybrook scale at month 1 is 100. If sunnybrook at month 1 $\leq$ 99 then patients are considered as not healed (0)	Month1_SB_healed
Complete recovery of palsy at month 12 according to SB scale	Healed (1) if sunnybrook scale at Month 12 visit is 100. If sunnybrook at Month 12 visit $\leq$ 99 then patients are considered as not healed (0)	Month12_SB_ghealed
Complete recovery of palsy at month 1 according to HB scale	Healed (1) if HB scale at Month 1 visit =1. If HB scale at Month 1 visit >1 then patients are considered as not healed (0)	Month1_HB_healed
Complete recovery of palsy at month 12 according to HB scale	Healed (1) if HB scale at Month 12 visit =1. If HB scale at Month 12 visit >1 then patients are considered as not healed (0)	Month12_HB_healed
Compliance (%)	Compliance in % = (total number of capsules (10) minus Number of capsules remaining) * 100/10 (0% - 100%)	Compliance_pct

FaCE scale (Total score will be used)

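### The set the SAP calls ITT is a modified ITT with conditions applied after randomisation, and the compliance variable in SAP 12 conflicts with the SAP 8.3 formula behind the compliance exclusions

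*SAP*

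**What the plan says.** **Analysis set.** Protocol 13.2 states: "Intention-to-treat will be applied when analyzing results from the primary outcome". It does not define the set. Its last paragraph says that patients "screened but not received any study medication, will be considered as screen failures and will not be included in the study database". Protocol 13.1 instead equates screening failures with subjects who were not randomised. SAP 7 repeats the no-product definition of a screening failure and gives the ITT set as "All randomized patients receiving at least one dose of study drug and have available data", to be used for both efficacy and safety. SAP 8.3 adds: "Patients with 0% compliance will be excluded from ITT analysis". SAP 11 lists no change from the planned analysis.

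**Order of events.** Under protocol 9.4 an eligible child receives a randomisation number together with the bottle carrying that number. The 10-day course is then taken from that bottle.

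**Compliance.** SAP 8.3 divides the capsules taken by the total number of capsules; its weight table sets that total at 20 to 100. It adds: "All bottles include 100 capsules". It also says: "Patients with treatment compliance less than 70% will be excluded from the PP analysis". SAP 12 defines the SAS variable Compliance_pct from "total number of capsules (10) minus Number of capsules remaining", multiplied by 100/10. Protocol 10.8 measures accountability by counting what is left in the bottle.

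**The concern.** An intention-to-treat analysis keeps every randomised child in the assigned arm. Here a child can leave the primary set for something that happens after allocation: taking no capsule, or lacking data in a sense the SAP does not define. The primary result would carry a label it has not earned. If undosed children are also treated as screening failures, they are absent from the database and no later analysis can restore them.

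The compliance variable matters because two exclusions depend on it: the 0% rule for ITT and the 70% rule for per protocol. Two formulas for one quantity mean that the programmer's choice decides who is analysed, and under SAP 12 the error depends on body weight.

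**Working it through.** **1. Design figure.** For 80% v 90% recovery at two-sided 5%, exact Fisher power at 215 per arm is 0.803. This reproduces the SAP 9 total of 430 for 80% power. At 250 per arm with no loss it is 0.863. The sample size is not in dispute.

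**2. Effect of leaving out undosed children.** The documents give no undosed share, so I assume u = 1% to 5% per arm, undosed children recovering at 80% in both arms, and no other loss.
- All randomised, 250 per arm: the prednisolone rate is 0.90(1 − u) + 0.80u, i.e. 89.9% at 1% and 89.5% at 5%. Power is 0.8547 and 0.8186.
- Dosed only, 80% v 90%: 250 × 0.99 ≈ 248 and 250 × 0.95 ≈ 238 per arm. Power is 0.8598 and 0.8427.
- Difference: 0.8598 − 0.8547 = 0.005, and 0.8427 − 0.8186 = 0.024.

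Outer bound: every undosed child also has no post-baseline grade and counts as not recovered. The rates become 80% × 0.99 = 79.2% v 90% × 0.99 = 89.1%, or 80% × 0.95 = 76% v 90% × 0.95 = 85.5%. Power is 0.839 at 1% and 0.740 at 5%.

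**3. The two compliance formulas.**
- SAP 8.3: taken × 100 / prescribed total.
- SAP 12: (10 − remaining) × 100/10.

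No weight band has a total of 10. 'Remaining' can be read as (a) the count in the 100-capsule bottle, as protocol 10.8 suggests, or (b) what is left of the prescribed total.

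| Weight (kg) | Prescribed total | Full compliance, SAP 8.3 | Full compliance, SAP 12 (a) | Full compliance, SAP 12 (b) | One day missed, SAP 8.3 | One day missed, SAP 12 (b) |
|---|---|---|---|---|---|---|
| 5–9.9 | 20 | 100% | −700% | 100% | 90% | 80% |
| 10–14.9 | 30 | 100% | −600% | 100% | 90% | 70% |
| 15–19.9 | 40 | 100% | −500% | 100% | 90% | 60% |
| 20–24.9 | 50 | 100% | −400% | 100% | 90% | 50% |
| 25–29.9 | 60 | 100% | −300% | 100% | 90% | 40% |
| 30–34.9 | 70 | 100% | −200% | 100% | 90% | 30% |
| 35–39.9 | 80 | 100% | −100% | 100% | 90% | 20% |
| 40–44.9 | 90 | 100% | 0% | 100% | 90% | 10% |
| >45 | 100 | 100% | 100% | 100% | 90% | 0% |

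Example for (a), 20 capsules: 80 remain, so (10 − 80) × 10 = −700%. Example for (b), 40 capsules with one day (4 capsules) missed: (10 − 4) × 10 = 60%.

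Under (a), eight of nine bands fall below 70% at full compliance, and the 40–44.9 kg band lands exactly on the ITT exclusion value. Under (b), one missed day falls below 70% in seven of nine bands. In the >45 kg band the two readings coincide because the prescribed total is the whole bottle: 90 of 100 taken gives (10 − 10) × 10 = 0%, against 90% under SAP 8.3.

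**The case against.** **Protocol 13.2 contradicts itself.** A reader might infer this from the intention-to-treat promise and the screening-failure rule in one section. The text does not force it. If 'received' means dispensed, every randomised child has received medication and 13.2 agrees with 13.1. The protocol is ambiguous. It is the SAP, through the one-dose requirement and the 0% rule, that settles on 'taken'. The data-availability and 0% conditions appear only in the SAP.

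**The data condition removes children whom SAP 8.8 would impute.** That would follow if it meant a 12-month grade. The likelier meaning is any collected data: the SAP 7 Withdrawals row concerns children who leave before data collection, and the per-protocol definition uses a different term. The wording is undefined; it is not shown to be a wrong exclusion.

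**Fully compliant children will certainly be dropped.** That holds only on the bottle-count reading. The two formulas agree if '10' and 'remaining' are daily doses, but SAP 12 says capsules. SAP 12 also states a 0–100% range, so negative values would probably be noticed in programming. It is evidently a drafting slip. What stands is that neither capsule reading scores partial compliance correctly.

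**The 0% rule misses undosed children.** Under SAP 12 a never-dosed child with a full bottle scores (10 − 100) × 10 = −900%. This changes nothing, because SAP 7 separately requires a dose.

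**Little is gained.** The SAP prints its definition openly and reports population membership by arm, and relabelling the set would cure the name. That is fair on size. It would not keep undosed children in the database or give the intention-to-treat analysis the protocol promises.

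**Conclusion.** The concern holds, and the plan should be changed. The SAP's ITT set is a modified ITT, so it does not deliver what protocol 13.2 promises. The documents do not support a claim of serious bias. With blinded treatment and few undosed children it is probably small, and the power difference of 0.005–0.024 rests on my assumed 1–5% undosed per arm.

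The formula conflict is definite, but its consequence depends on how 'remaining' is read. On the bottle count, compliant children leave the per-protocol set in eight of nine bands, and those at 40–44.9 kg leave ITT. On the prescribed-total reading the harm is confined to children who miss capsules. On either, a child above 45 kg who took 90% of the course scores 0%.

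**What to change.** **Analysis set (SAP 7, 8.3; protocol 13.2).**
- Define ITT as all randomised children analysed as assigned, whatever their dosing or compliance.
- Handle a missing 12-month House-Brackmann grade by SAP 8.8. Count a child with no post-baseline grade as not recovered, unless consent to use the data is withdrawn. Worst-case carry-forward largely implies this already. Stating it also covers a child who leaves before the first grading, which protocol 8.2 allows one day after admission.
- Delete the data-availability condition and the 0%-compliance exclusion from ITT.
- State in SAP 7 and protocol 13.2, in line with 13.1, that a randomised child is never a screening failure and stays in the database.
- Use a separately named dosed set for safety and, if wanted, for supportive efficacy.

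**Compliance (SAP 12).** Replace the formula with that of SAP 8.3: (100 − capsules returned) / the child's prescribed total × 100. If the bottle is not returned, set compliance to missing. Taking returns as zero would give a 20-capsule child 100/20 × 100 = 500%.

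**Cost.** Wording changes to a SAP whose version history shows only Draft 1.0, and a short protocol clarification. The statistical price is slight dilution from never-dosed children. At the outer bound, power would be 0.839 (1% undosed) or 0.740 (5%), against 0.860 and 0.843 for the dosed set. The 5% figure is below the design's 80%, but only if every undosed child also lacks a post-baseline grade.
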